11.4.1 Positive Urinalysis Treatment and Rescreening

Subjects who are excluded as a result of a positive urinalysis may be treated and rescreened at a future visit.

11.5 Expected Individual Subject Participation and Total Duration of the Clinical Investigation

The estimated time needed to meet the enrollment requirement is 4 months.

The study will consist of a 90 day treatment period. Subjects may be screened and fitted with a Spanner stent at Visit 1. The stent will be replaced at an interval of approximately 30 days (25-35 days permitted) for a total of up to 90 days of use (75-105 days permitted). Subjects will complete the study upon removal of the Spanner stent after 90 days and one follow-up telephone call post-removal.

The expected total duration of this clinical investigation is 8 months.

11.6 Number of Subjects Required

Assuming a dropout rate of 20%, the total sample size of n=105 subjects will be required for the study.

12 PROCEDURES

12.1 Study Activities Table

The study activities are listed in **Table 5**. Further descriptions of the study activities are provided in this section

Table 5. Study Activities					
Activity	Visit 1 Screening, End of Catheter use (Stent #1 Placement)	Visit 2 1 Month (Stent #1 Removal. Stent #2 Placement)	Visit 3 2 Month (Stent #2 Removal. Stent #3 Placement)	Visit 4 3 Month (Stent #3 Removal)	Follow-up Phone Call
Visit Windows	Not Applicable	30 ± 5 days	30 ± 5 days	30 ± 5 days	15-20 days post Final Stent Removal
Informed Consent	√				
History and Physical with DRE	√				
Urinalysis with Micro	√	√	√	√	
Urine Culture & Sensitivity (If indicated)	√	√	√	√	
Uroflow	√	√	√	√	
PVR	√	√	√	√	
Subject Satisfaction Questionnaire	√	√	√	√	
IPSS		√	√	√	
Cystoscopy	√			√	
Patient is enrolled	√				
Urethral length measurement with Surveyor	√				
Stent Placement	√	√	√		
Serum Creatinine	√	√	√	√	
Adverse Events	√	√	√	√	√
Discharge					√

CONFIDENTIAL

12.1.1 Visit 1: Screening, End of Catheter Use and Stent #1 Placement

- Obtain informed consent.
- Obtain the medical history and perform a physical examination including a digital rectal examination.
- Confirm that subject is not taking anticholinergic medication to manage bladder spasm (an exclusion criterion).
- To obtain a urine specimen:
- Remove the catheter
- Allow the subject to naturally fill his bladder
- Obtain and send a urine specimen for UA & UC&S if indicated.
- Confirm that the UA is negative.
- Perform cystoscopy and take two cystoscopy photographs: (a) of the bulbar urethra looking at a closed external sphincter, and (b) at the verumontanum looking towards the bladder.
- Subjects who meet the inclusion and exclusion criteria will be enrolled into the study.
- For directions for Spanner size selection and insertion refer to *The Spanner Physician Instructions for Use* (see **Attachment A**). Use the Surveyor urethral measurement device to determine the appropriate size Spanner.
- Insert the Spanner.
- Place cystoscope into bulbar urethra and confirm the proper location of the distal anchor. If the Spanner was incorrectly sized, the stent can be removed and replaced with the proper size. Replacement may occur one time only.
- Record any Adverse Event that occurred during sizing and Spanner insertion.
- Allow the subject to drink fluids and wait for a full bladder. Alternatively, investigator may choose to fill the bladder using cystoscopy (if cystoscopy filling is performed, note in the source and the eCRF system).
- With Stent #1 in place, perform the uroflow test followed by measurement of the PVR (abdominal ultrasound). Refer to **Attachment B** for requirements for uroflow testing.
- Provide *Subject Information Booklet for The Spanner* (see **Attachment D**) to the subject. Review each potential Adverse Event with the subject and the appropriate actions to be taken by the subject if they occur.
- Provide *Subject Emergency Removal Card* (see Attachment D) to the subject. Instruct the patient to provide the card to other care providers to inform them that the patient is wearing the Spanner.
- Obtain and send blood sample for serum creatinine.
- Have the subject complete the subject satisfaction questionnaire.
- Interview the subject for signs and symptoms of Adverse Events.
- Place test reports in the subject's study file and record in eCRF..
- Schedule the subject to return for Visit 2 (in 25-35 days).

CONFIDENTIAL

12.1.2 Visit 2: Stent #1 Removal and Stent #2 Placement

- Have the subject complete the subject satisfaction questionnaire and an IPSS survey. Instruct the subject that he should answer the questions about symptoms related to the timeframe between visits.
- Obtain and send a urine specimen for UA & UC&S (if indicated). Place a copy of the test report in the subject's study file and record in eCRF.
- Perform a uroflow test. Measure and record the Qmax during the test. Refer to **Attachment B** for requirements for uroflow testing. Place the uroflow report in the subject's study file.
- Immediately following each uroflow test, measure the PVR using abdominal ultrasound. Record the PVR with the corresponding uroflow test. Note: If two uroflow tests were conducted PVR must be measured and reported for each test.
- Remove Stent #1
- Place Stent #2.
- Obtain and send blood sample for serum creatinine.
- Interview the subject for signs and symptoms of Adverse Events.
- Schedule the subject to return for Visit 3 (in 25-35 days).

12.1.3 Visit 3: Stent #2 Removal and Stent #3 Placement

- Have the subject complete the subject satisfaction questionnaire and an IPSS survey. Instruct the subject that he should answer the questions about symptoms related to the timeframe between visits.
- Obtain and send a urine specimen for UA & UC&S (if indicated). Place a copy of the test report in the subject's study file and record in eCRF.
- Perform a uroflow test. Measure and record the Qmax during the test. Refer to Attachment B for requirements for uroflow testing. Place the uroflow report in the subject's study file and record in eCRF.
- Immediately following each uroflow test, measure the PVR using abdominal ultrasound. Record the PVR with the corresponding uroflow test. Note: If two uroflow tests were conducted PVR must be measured and reported for each test.
- Remove Stent #2
- Place Stent #3.
- Obtain and send blood sample for serum creatinine.
- Interview the subject for signs and symptoms of Adverse Events.
- Schedule the subject to return for Visit 4 (in 25-35 days).

12.1.4 Visit 4: Stent #3 Removal

- Have the subject complete the subject satisfaction questionnaire and an IPSS survey. Instruct the subject that he should answer the questions about symptoms related to the timeframe between visits.
- Obtain and send a urine specimen for UA & UC&S (if indicated). Place a copy of the test report in the subject's study file and record in eCRF.

CONFIDENTIAL

- Perform a uroflow test. Measure and record the Qmax during the test. Refer to Attachment B for requirements for uroflow testing. Place the uroflow report in the subject's study file and record in eCRF.
- Immediately following each uroflow test, measure the PVR using abdominal ultrasound. Record the PVR with the corresponding uroflow test. Note: If two uroflow tests were conducted PVR must be measured and reported for each test.
- Remove Stent #3
- Perform cystoscopy and take two cystoscopy photographs: (a) of the bulbar urethra looking at a closed external sphincter, and (b) at the verumontanum looking towards the bladder.
- Obtain and send blood sample for serum creatinine.
- Interview the subject for signs and symptoms of Adverse Events.
- Schedule the subject for a follow-up phone call (in 15-20 days).

12.1.5 Phone Call #1

- Via telephone, interview the subject for signs and symptoms of Adverse Events. Record information on the Adverse Event eCRF.
- Discharge subject from study.

NOTE: Any subject with an ongoing or unresolved adverse event may continue to be followed until the event is resolved. The subsequent follow up and resolution should be documented on the Adverse Event eCRF.

12.1.6 Unscheduled Visits

If the subject returns to a medical facility due to a BPH or stent related issue, then complete an Unscheduled Visit eCRF.

12.1.7 Post Study Completion - Continued Access

If, at the completion of all study visits, the Spanner is not yet approved for this indication, then the investigational device may be made available during the preparation and review of the marketing application, to allow enrolled subjects to extend their use of the device.

These continued access visits will be conducted in compliance with the clinical investigational plan, ISO 14155, and 21 CFR Parts 812, 50, 54, and 56. The study visits will be conducted by the delegated study staff using the eCRFs, including visit, unanticipated visit, and adverse event monitoring. There will be continued CRO oversight and monitoring during this entire continued access period and additional safety and effectiveness data will be collected.

Subjects must have completed the requirements of the final telephone visit described in Section 12.1.5 above before obtaining voluntary continued access. Subjects who volunteer for continued access will be required to attend monthly study visits (30 days +/- 5 days) repeating the requirements of Visit 3 (the Continued Access Visit requirements are listed below). These visits may continue until use of the Spanner is no longer clinically indicated or desired, or until the Spanner receives marketing approval for this indication, whichever is sooner.

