12.1.7.1 Continuing Access Visits after Study Completion: Stent Removal and Placement

- Have the subject complete the subject satisfaction questionnaire and an IPSS survey. Instruct the subject that he should answer the questions about symptoms related to the timeframe between visits.
- Obtain and send a urine specimen for UA & UC&S (if indicated). Place a copy of the test report in the subject's study file and record in eCRF.
- Perform a uroflow test. Measure and record the Qmax during the test. Refer to Attachment B for requirements for uroflow testing. Place the uroflow report in the subject's study file and record in eCRF.
- Immediately following each uroflow test, measure the PVR using abdominal ultrasound. Record the PVR with the corresponding uroflow test. Note: If two uroflow tests were conducted PVR must be measured and reported for each test.
- Remove Stent
- Place Stent.
- Obtain and send blood sample for serum creatinine.
- Interview the subject for signs and symptoms of Adverse Events.
- Schedule the subject to return for next Visit (in 25-35 days).

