16. CONTINUING ACCESS PROTOCOL

Most of the tables providing summary data from the Continuing Access Protocol (CAP) are similar to the tables from the pivotal study.

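### Continued access lists no removal-only visit and no post-removal adverse-event call, and its adverse-event tables carry no stated exposure time, so they cannot be read against the main study's tables.

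*Protocol*

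**What the plan says.** Protocol 12.1.7 lets men who have finished the study go on using the device while the marketing application is prepared and reviewed. On entry: "Subjects must have completed the requirements of the final telephone visit described in Section 12.1.5 above before obtaining voluntary continued access". On schedule: "Subjects who volunteer for continued access will be required to attend monthly study visits (30 days +/- 5 days) repeating the requirements of Visit 3". On duration, where the earlier event governs and the approval meant is for the use under study: "These visits may continue until use of the Spanner is no longer clinically indicated or desired, or until the Spanner receives marketing approval for this". The section says that further safety and effectiveness data will be gathered and that visits are run "using the eCRFs, including visit, unanticipated visit, and adverse event monitoring".

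Section 12.1.7.1 gives the only CAP visit list. It has the satisfaction questionnaire, IPSS, urinalysis (with culture if indicated), uroflow, PVR, removal of one stent, placement of another, creatinine and the step "Interview the subject for signs and symptoms of Adverse Events". Its last step is "Schedule the subject to return for next Visit (in 25-35 days".

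The main study ends differently. Section 12.1.4 (Visit 4) removes the third stent, places none, performs cystoscopy and books a call 15-20 days later. Section 12.1.5 uses that call to ask about adverse events.

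The SAP opens Section 16 with "Most of the tables providing summary data from the Continuing Access Protocol (CAP) are similar to the tables from the pivotal study". Sections 16.7 and 16.8 name Tables 58 and 59 for CAP adverse events, overall and related, to be summarized as in SAP Section 8 (counts and percentages).

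**The concern.** CAP is the plan's only source of data beyond the 75-105 stent days of the main study. Protocol 10.1 notes that current US labeling does not foresee replacing the first stent at all, so safety under repeated replacement is what a reader will look for here.

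Two kinds of event can escape the CAP schedule. One is an event that appears after the last stent is out. The other is an anatomical change without symptoms. Section 7.2 lists injury to the bladder or urethra among the anticipated effects, and Section 9 says the closing cystoscopy is there to detect effects on anatomy. The main study has a scheduled assessment for both kinds; CAP has neither.

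The SAP then summarizes CAP events in the same descriptive style. Section 16 mentions neither time at risk, which differs between men in CAP, nor the different ascertainment. A reader who sets Table 58 or 59 beside the main-study tables would be comparing figures with different exposure and different looking.

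**Working it through.** **1. The plan's own calendar.** Three placements of 25-35 days give 3 × 25 = 75 to 3 × 35 = 105 stent days, as stated. Adding 20 days to the call gives 105 + 20 = 125 days, which matches the stated maximum participation (Protocol 9; SAP 5.4).

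**2. End-of-use assessments side by side.**

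| | Main study (12.1.4-12.1.5) | CAP (12.1.7-12.1.7.1) |
|---|---|---|
| Adverse-event interview at each monthly visit | yes | yes |
| Urinalysis, PVR, creatinine at each monthly visit | yes | yes |
| Removal-only visit | yes (Visit 4) | none listed |
| Scheduled cystoscopy after last removal | 1 | none listed |
| Adverse-event call after last removal | at 15-20 days | none listed |
| Adverse-event displays named in the SAP | 5 (Tables 40-44) | 2 (Tables 58-59) |

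The CAP list names no serious-event or by-visit display; disposition is covered by Table 52.

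**3. How much observation the call adds.** With 90 stent days, the post-removal window is 15/(90 + 15) = 14% to 20/(90 + 20) = 18% of scheduled time. A man with 360 CAP stent days would gain 15/375 = 4% to 20/380 = 5%. As written, CAP schedules 0 post-removal days.

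**4. Direction of any difference.** The documents give no event rates, so these are assumptions: monthly probability of an event found at interview, p = 5-20%; probability found only at the closing cystoscopy, q = 0-20%; probability found only at the call, c = 0-5%. True risk is the same in both phases.

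- Per-subject percentage, main study: 1 − (1 − p)³(1 − q)(1 − c).
- Per-subject percentage, CAP after m months: 1 − (1 − p)^m.
- With p = 10% and q = c = 5%, the main study gives 1 − 0.729 × 0.95 × 0.95 = 34.2%. CAP gives 27.1% at 3 months, 34.4% at 4 and 46.9% at 6.
- Over the whole assumed range, CAP reaches or passes the main-study percentage after 3 to 9 months.
- Events per stent-month: main study (3p + q + c)/3, CAP p. For the same example, 0.40/3 = 0.133 against 0.100, a ratio of 0.75. Over the range the ratio runs from 0.38 to 1.00, and it equals 1.00 only when q = c = 0.

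**5. Whether adding the call alone restores comparability.** With p = 10%, q = 0, c = 5% and 12 CAP months, CAP gives (12 × 0.10 + 0.05)/12 = 0.104 per stent-month and the main study (0.30 + 0.05)/3 = 0.117. If call-only events are dropped from the main study alone, it becomes 0.100 against 0.104, and the bias reverses. The restriction must be the same on both sides.

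**The case against.** The case against is substantial, and most of it stands.

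- **CAP is not unobserved.** Every visit has an interview and laboratory checks, and unscheduled visits are recorded. Section 21.5 advises cystoscopy after removal for persistent gross hematuria or severe pain, and cystoscopy or x-ray for suspected migration or retention. This confines the gap to silent findings and events after the last removal.
- **Section 11.3 might fill it.** It asks, where possible, for the Visit 4 evaluations on premature withdrawal. A man whose CAP use ends because the device is approved, or is no longer needed, has not withdrawn prematurely, and he was already discharged from the study at the call. The text does not say that 11.3 applies to him.
- **No comparison is planned, and the table templates are a separate document (SAP 3.2) that is not available here.** Both are true. Whether Tables 58-59 already show exposure cannot be confirmed; SAP Section 16 does not say so.
- **Cystoscopy findings may add little to the main-study event tables.** The SAP names cystoscopy tables only at baseline (Tables 20-22), so a Visit 4 finding reaches those tables only if it is recorded as an adverse event. q could be near zero.

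A reader might infer that CAP harm must look lower by construction. The documents do not support that: SAP Section 8 plans percentages per subject, these accumulate with exposure, and the example above goes either way. Nor does CAP run indefinitely, since end conditions are written. A lower CAP rate could also reflect selection, because only men who completed the study and volunteered can enter.

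**Conclusion.** The gap is in the text and is narrow. CAP schedules no removal-only visit and no post-removal adverse-event call, and no other section clearly supplies them when a man leaves CAP. What may be missed is events after the last removal and silent anatomical change.

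As described in SAP 16.7-16.8, the CAP adverse-event tables cannot be read against the main-study tables, because exposure and ascertainment both differ and neither is stated. The size and, for per-subject percentages, even the direction of any distortion cannot be derived from the documents. The 0.38-1.00 range for the per-month ratio and the 3-9 month crossover rest wholly on the assumed p, q and c and on equal true risk.

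The primary and secondary endpoints of the 90-day study are not affected. The point is still worth settling before CAP starts, because post-removal observation that is not made cannot be recovered later.

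**What to change.** 1. **Protocol.** Reconcile 11.3, 12.1.4-12.1.5 and 12.1.7 so that they state which end-of-use assessments apply when a man leaves CAP for any reason. Apply the existing 15-20 day adverse-event call, on the existing form CRF06, after the last CAP stent removal. Whether a closing cystoscopy is included is for the sponsor to decide; it is an added procedure with its own risks (Protocol 7.4).
2. **SAP 16.7-16.8.** Report total stent-months and events per stent-month alongside the counts and percentages.
3. **CAP tables.** State that ascertainment differs from the main study, including that no cystoscopy was scheduled unless one is added. If CAP and main-study rates are shown together, restrict both to events detected while a stent is in place or at the monthly visits, with the same exclusion on each side. Item 2 without this restriction would tend to make CAP look low.

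The cost is one phone call per CAP participant, some wording and a small amount of extra tabulation. The restricted display also needs to know how an event was found, which is not among the items in SAP 14.1.1. Onset dates can separate some events that began after the last removal; findings seen only at cystoscopy would need a flag.

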12.1.7.1 Continuing Access Visits after Study Completion: Stent Removal and Placement

- Have the subject complete the subject satisfaction questionnaire and an IPSS survey. Instruct the subject that he should answer the questions about symptoms related to the timeframe between visits.
- Obtain and send a urine specimen for UA & UC&S (if indicated). Place a copy of the test report in the subject's study file and record in eCRF.
- Perform a uroflow test. Measure and record the Qmax during the test. Refer to Attachment B for requirements for uroflow testing. Place the uroflow report in the subject's study file and record in eCRF.
- Immediately following each uroflow test, measure the PVR using abdominal ultrasound. Record the PVR with the corresponding uroflow test. Note: If two uroflow tests were conducted PVR must be measured and reported for each test.
- Remove Stent
- Place Stent.
- Obtain and send blood sample for serum creatinine.
- Interview the subject for signs and symptoms of Adverse Events.
- Schedule the subject to return for next Visit (in 25-35 days).

12.2 Foreseeable Factors that May Compromise the Outcome of the Clinical Investigation

CONFIDENTIAL

Use of anticholinergic medication to manage bladder spasm is an exclusion criterion. Subjects taking anticholinergic medication are asked to discontinue use of the medication for the duration of the study.

The inclusion assessment requires evidence of detrusor muscle contractility. Subjects entering the study with poor bladder contractility could result in unanticipated device failures.

13.2 Monitor Responsibilities

A sponsor may designate one or more appropriately trained and qualified individuals to monitor the progress of a clinical investigation. A monitor need not be a person qualified to diagnose and treat the disease or other condition for which the test article is under investigation, but somewhere in the direct line of review of the study data there will be a person so qualified.

Each monitor will be trained on monitoring per Standard Operating Procedures (SOPs), the protocol and protocol-specific monitoring plan prior to conducting any study-specific activities.

13.3 Procedures

SRS Medical is responsible to ensure that the study is monitored and to confirm proper conduct and progress of the study including adequate protection of human subjects and the integrity of the clinical study data is of the highest quality. The sponsor shall assess the extent and nature of monitoring appropriate for the clinical investigation, including the strategy for source data verification, based on considerations such as the objective, design, complexity, size, critical data points and endpoints of the clinical investigation. Results of this assessment shall be used to develop a monitoring plan.

The monitor shall have access to the source documents and other information needed to ensure investigator compliance with the clinical investigation plan and applicable rules and regulations, and to assess the progress of the clinical investigation.

Site visits will be made before the study begins, at regular intervals during the study, and at the study closeout. Communication by telephone, mail, and e-mail may be used as needed to supplement site visits. The investigator and study personnel will cooperate with the sponsor and their representatives, provide all appropriate documentation, and be available to discuss the study.

CONFIDENTIAL

13.4 Monitoring and Audit Visits

Site visits will be made before the study begins, at regular intervals during the study, and at the study closeout. Communication by telephone, mail, and e-mail may be used as needed to supplement site visits. The Investigator and study personnel will cooperate with the sponsor and their representatives, provide all appropriate documentation, and be available to discuss the study. Adequate time and space for these visits should be allocated by the investigator.

According to the guidelines on Good Clinical Practice, the monitor will check the CRF entries against the source documents. The consent form will include a statement by which the subjects allow the sponsor's duly authorized personnel to have direct access to source data which supports data on the case report forms (e.g.: medical records, clinic charts and office notes, appointment books, original laboratory records, uroflow printouts, cystoscopy reports, etc.). These personnel, bound by professional confidentiality, will not disclose any personal identity or personal medical information outside of the realm of study data.

The monitoring and auditing visits may include but are not limited to the following:

